## Ethical Considerations relating to the Clinical Trial including the expected Benefit to the individual Subject or Group of Patients represented by the Trial Subjects as well as the Nature and Extent of Burden and Risks

This study will provide more insight in a combination treatment for patients suffering from chronic pain and determine if the addition of nortriptyline is better than morphine alone. Morphine and nortriptyline are registered drugs which are widely used in the clinic, amongst other analgesics. The safety profiles of these compounds are well known. Both analgesic and adverse effects are likely to occur. Symptoms such as sedation, somnolence, dizziness, fatigue, reduced vigilance, are to be expected following administration for both compounds, but will be closely monitored by medically trained staff as part of the study objectives.

This study will produce novel information on the clinical utility of morphine and nortriptyline when coadministered, i.e., potentiation of analgesic effects (profiled using PainCart®) and characterization of side effect profile (using CNS biomarkers and NeuroCart®).

Study subjects will undergo a medical screening and eligibility will be checked multiple times before administering the study drug. During the clinical study, administration will be done in the clinic under medical supervision. Subjects will be closely monitored and will be discharged by a physician from the unit only if their medical condition allows. In case of nausea and/or vomiting anti emetic, treatments will be administered with metoclopramide 10 mg intravenously as a single dose, which can be repeated if nausea or vomiting persists.

At doses above 3 mg, morphine may decrease respiration in dose-dependent manner. While the dose of 7mg be administered are expected to be manageable. The total maximum dose of morphine IV on a single day is expected to provide adequate analgesic properties and measurable effects on neurocognitive tests, while having manageable adverse effects. As an additional safety measure, oxygen saturation will be measured after the first morphine administration at fixed timepoints as indicated in the Schedule of Assessments, and additionally when deemed necessary.

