The measurement techniques performed in this study (PainCart® and CNS tests) are considered to be safe and with minimal risk. Capsaicin application on the volar forearm may cause some transient skin irritation on the application site. The skin may become red and/or more sensitive to e.g., warm water, and to touch (a slight burning sensation). After one or two days the effects will generally resolve.

**Table 1.** Visit and Assessment Schedule

	SCR		Treatment period 1 - 4 								FU 						
	SCR	Day -1						С	Day 1							Day 2	
Time point Assessment	Up to -42 d to -5 days	Day -1	Pre- dose	0 h	1h	2 h	3 h	3.5 h	4 h	5 h	6 h	6.5 h	7.5 h	8 h	9 h	24 h	+14 d ± 2 d
Informed consent	Х																
Demography	х																
Inclusion and exclusion criteria	х		х														
Medical history	х																
Height, Weight³, BMI	х																Х
Admission to clinic		Х															
Physical examination 	х		X 														Х
Virology	х																
BsHaem, BsChem, BsGluc, Urinalysis	х	х															Х
UrDrug, BrAlc, UrPreg 	х	Х															Х
Temperature	х	Х	Х													Х	Х
ECG	х		Х											х		х	Х
General symptoms	х		Х		х	х				х				х		х	
Vital Signs (Pulse Rate, BP, RR, O 2 saturation) 			х							х		Х		х		х	Х
Meals / snack 			X8		х				х					х	х	х	
Drug (-placebo) administration				х		х				х							
PK sample			Х		х	X 9			х	X 9	х			х		х	
Capsaicin application	X 		X 														
Capsaicin task – Von Frey test 			х		х		х		Х		х		Х		Х		
PainCart®12,13	X 		X 		Х		Х		Х		Х		Х		Х		
NeuroCart®12	X 		X 		х	х		х		х		Х			х		
pEEG			X 			Х				Х		Х			Х		

VVLT 	х					х			Х					
STAI	х		х		х	х		Х	Х	Х		Х		
BSI		Х										Х		
Discharge	Х												X 	
(S)AE			continuous						Х					
Concomitant medication	Х		continuous						Х					

BP = Blood Pressure, HR = Heart Rate, RR = Respiratory Rate, SCR = Screening, EEG = Electroencephalogram, PK = Pharmacokinetics, AE = Adverse Event, (S)AE = Serious Adverse Event, UrDrug = Urine Drug Screen, UrPreg = Urine Pregnancy test, BsHaem = Blood Sample Haematology, BsChem = Blood Sample Chemistry, BsGluc = Blood Sample Glucose, BsBiomarker = Blood Sample Biomarker, BrAlc = Breath Alcohol Test., BMI = Body Mass Index

- At least 7 days between treatment periods

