- Follow up (FU) visit after last treatment.
- Only weight will be measured at FU or upon early termination
- Physical examination at screening includes assessment of the Fitzpatrick skin type and evaluation of acne, freckles, tattoos or scarring on the back.
- A symptoms based physical examination will be performed.
- For women of childbearing potential: Urine beta HCG will be performed either during screening, on the first day of each treatment period or the day before the first day of each
- Treatment Period at discretion of Investigator. In either case, the results must be negative prior to dosing study participants.

  Vital signs will be measured in supine position. Oxygen saturation will be monitored after dosing at 2h until the end of study day 1 of each treatment period.
- Lunch at 0.5h and dinner 8h post dose, snack at 4.5h, time points are indicative. Light breakfast on Day 1 is shortly after wake activity around -3.5hours, after breakfast the subject starts fasting until after dosing. No meal restrictions on day -1 and day 2.
- PK sample taken 3 minutes after dosing
- Capsaicin application at screening must be performed on or before Day -5 to ensure sufficient washout between the capsaicin that is applied at screening and applied on Day 1.
- Capsaicin application will only be performed after enrolment in subjects not allergic or intolerable to the capsaicin solution, as determined at screening
- Sequence of assessments is NeuroCart® before PainCart®, for specific order of assessments see section 6.4.

  Capsaicin heat pain test (and heat pain test on control skin on volar forearm) will only be performed on subjects not allergic or intolerable to the capsaicin solution. Capsaicin heat pain task only applicable for Day 1.

  PainCart® training up to 42 days before dosing and NeuroCart® training up to 21 days before dosing.
- PainCart® and NeuroCart® will be done twice for baseline measurement
- NeuroCart® round with pEEG measurement only in second baseline measurement
- VVLT at 2u post dose will be measured is the immediate recall. VVLT at 5u post dose will be the delayed recall and recognition.
- Discharge time is approximate and only when deemed safe.

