#### Morphine

Morphine appears to mimic the body's endorphins that are responsible for analgesia causing sleepiness, and feelings of pleasure. Morphine is a phenanthrene opioid receptor agonist which binds to and activates opioid receptors in the central nervous system and is studied extensively in clinical studies over the years. The most serious and very common side effect of morphine therapy is respiratory depression. Other very common side-effects are nausea, vomiting, constipation, drowsiness and dizziness. Tolerance generally develops with long term use; however this is not the case for constipation. (SPC morphine, section 4.8). Similar effects are observed in studies conducted in healthy volunteers, where the most frequently reported adverse effects were respiratory depression, constipation, sedation, dizziness, and nausea. 19,20

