Study subjects will undergo a medical screening and eligibility will be checked multiple times before administering the study drug. During the clinical study, administration will be done in the clinic under medical supervision. Subjects will be closely monitored and will be discharged by a physician from the unit only if their medical condition allows. In case of nausea and/or vomiting anti emetic, treatments will be administered with metoclopramide 10 mg intravenously in a single dose, which can be repeated if nausea or vomiting persists.

After administration of morphine and nortriptyline, it is not advised to drive a car or operate machinery for 48 hours after drug administration. Therefore, subjects participating in the study will be instructed not to drive a car and not to engage in activities that require operating vehicles or dangerous machinery for up to 48 hours following administration of the study drug. Thus, the subjects will remain in the clinic under supervision and will be discharged by a physician only if their medical condition allows.

[figure not shown]
At doses above 3 mg, morphine may decrease respiration in a dose-dependent manner. While the doses be administered are expected to be manageable. The total maximum dose of morphine IV on a single day is expected to provide adequate analgesic properties and measurable effects on neurocognitive tests, while having manageable adverse effects. As an additional safety measure, oxygen saturation will be measured after the first morphine administration at fixed timepoints as indicated in the Schedule of Assessments, and additionally when deemed necessary. The measurement techniques performed in this study (PainCart® and CNS tests) are considered to be safe and with minimal risk. Capsaicin application on the volar forearm may cause some transient skin irritation on the application site (only for eligible subjects). The skin may become red and/or more sensitive to e.g., warm water, and to touch (a slight burning sensation). After one or two days the effects will generally resolve.

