#### Vital signs

Evaluations of systolic and diastolic blood pressure, pulse rate, respiratory rate, oxygen saturation and temperature will be performed throughout the study. Pulse and blood pressure will be taken after 5 minutes in the supine position. Automated oscillometric blood pressures and pulse rate will be measured using a Dash 3000, Dash 4000, Dynamap 400, Dynamap ProCare 400, Nonin Xpod or Philips Intellivue MP70.

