### Vital signs

At each time point, absolute values and change from baseline of supine blood pressure and pulse rate will be summarized with n, mean, SD, SEM, median, Min, and Max values. The number of available observations and out-of-range values (absolute and in percentage) will be presented. Values outside the reference range will be flagged in the listing. 'H' and 'L', denoting values above or below the investigator reference range (when present), will flag out-of-range results.

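### The planned vital-signs summary leaves out respiratory rate and oxygen saturation, the measured signs of morphine's most serious named harm

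*Protocol*

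**What the plan says.** On the harm, section 2.2.2 (Clinical toxicology and safety pharmacology, Morphine) states: "The most serious and very common side effect of morphine therapy is respiratory depression". The ethical-considerations part of the synopsis adds that at doses above 3 mg "morphine may decrease respiration in dose-dependent manner". Both regimens include a 3 mg bolus at 2 h and a 7 mg bolus at 5 h.

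On collection, section 2.10.3 (Vital signs) states: "Evaluations of systolic and diastolic blood pressure, pulse rate, respiratory rate, oxygen saturation and temperature will be performed throughout the study". The vital-signs row of Table 1 also lists respiratory rate and oxygen saturation. The synopsis says "As an additional safety measure, oxygen saturation will be measured after the first morphine administration at fixed timepoints", section 2.3.2 repeats this, and a Table 1 footnote says "Oxygen saturation will be monitored after dosing at 2h until the end of study day 1 of each treatment period". Section 2.3.1 (Managing of effects) differs: it restricts oxygen saturation to cases where it is clinically indicated.

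On analysis, section 2.13.6 (Vital signs) says that "absolute values and change from baseline of supine blood pressure and pulse rate will be summarized". This applies to every time point and uses the usual descriptive statistics: the number of observations, the mean and median, the SD and SEM, and the lowest and highest value. The section then provides for counts and percentages of out-of-range values and for flagging against the investigator reference range. The opening safety paragraph of 2.13.6 has change from baseline calculated for every continuous safety parameter.

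**The concern.** Respiratory rate and saturation bear directly on the harm that the protocol itself puts first. They are measured for safety reasons and then drop out of the one paragraph that says how vital signs will be summarised. The synopsis makes a comparison of tolerability a secondary objective, and the design gives every subject morphine alone and morphine plus nortriptyline. Sedation is expected with both drugs, so readers of the report will want to know whether breathing differs between the two regimens. A report that follows the plan would show descriptive statistics for blood pressure and pulse but would have no instruction to show them for breathing rate or saturation.

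**Working it through.** The protocol gives no figure to reproduce. The check compares what is collected with what is summarised, then counts the values affected.

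**1. Collected against summarised**

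| Measure | Collected (2.10.3) | Named in the 2.13.6 summary |
|---|---|---|
| Systolic blood pressure | yes | yes |
| Diastolic blood pressure | yes | yes |
| Pulse rate | yes | yes |
| Respiratory rate | yes | no |
| Oxygen saturation | yes | no |
| Temperature | yes | no |

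Six measures are collected and three are named. Two of the three left out are the direct measures of respiratory depression. No other analysis paragraph names either of them.

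**2. Is the list meant to be closed?** The neighbouring paragraphs of 2.13.6 use class terms: ECG numeric variables for the ECG, and clinical laboratory variables for the laboratory. Only the vital-signs paragraph lists individual variables. It is also narrower than the opening safety paragraph, which has change from baseline calculated for all continuous safety parameters. Calculating a variable does not commit anyone to reporting it.

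**3. Values affected.** In Table 1 the vital-signs row is marked, within each period, at pre-dose, 5 h, 6.5 h, 8 h and 24 h.

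- Respiratory rate: 24 subjects × 2 periods × 5 time points = 240 scheduled values.
- Oxygen saturation: also 24 × 2 × 5 = 240 if it is taken whenever vital signs are taken, plus whatever is stored from the monitoring that starts at 2 h. If it is measured only on clinical indication, the number is unknown and could be far smaller.

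The count takes two periods, as in the synopsis design. Sections 2.5.2 and 2.5.3 speak of four.

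**4. What the schedule can support.** From the bolus at 2 h to the one at 5 h, the only scheduled respiratory-rate reading is the one at 5 h. Later on Day 1 there are two, at 6.5 h and 8 h. A lowest respiratory rate for the interval between the boluses would be the minimum of one reading.

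**The case against.** A reader might infer that respiratory depression has no between-treatment analysis at all. The protocol does not support that. The adverse-event paragraph of 2.13.6 tabulates treatment-emergent events by treatment, organ class and preferred term, then by severity and by relatedness, and Table 2 makes adverse events an endpoint of the safety objective. Respiratory depression recorded as an adverse event would therefore be compared. Nor can it be said that symptom-free falls in saturation would go unrecorded: section 2.12.1 defines an adverse event without requiring symptoms, uses daily activity only to grade severity, and recording follows a procedure that is not shown.

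Three further points stand against a stronger claim.

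- The vital-signs paragraph does not say that blood pressure and pulse are summarised by treatment, so there is no stated between-treatment summary for those either.
- Its out-of-range sentence names no variables and sits under a heading that elsewhere covers respiratory rate and saturation. On one reading those counts already include them.
- Means at fixed times can hide a fall in a few subjects, but the paragraph also asks for Min, Max and out-of-range counts, which would show such a fall if it occurred at a scheduled reading.

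It can also be said that the study is exploratory and that a statistical analysis plan may add the variables. That would settle a silent protocol. Here the protocol states a list that is too short, and a plan that follows it faithfully repeats the omission. Adverse-event counts also do not preserve the measured values.

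**Conclusion.** The point holds as a reporting gap. Measured respiratory rate and oxygen saturation have no stated descriptive summary, although the protocol collects both and names the harm they track as morphine's most serious. As written, the two regimens would be compared on respiratory depression only through adverse-event tables.

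The size is about 240 scheduled respiratory-rate values, and up to the same number of scheduled saturation values. Both figures assume two periods and the Table 1 time points as they read here; the second also assumes that saturation is recorded on schedule. The passages on saturation contradict one another, and until they are reconciled it is not known whether a complete set of values will exist to summarise.

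The documents do not support a demand for respiratory-rate nadirs by interval or for paired differences in nadirs with confidence intervals. With one scheduled reading between the boluses and two later on Day 1, these would add little to the fixed-time summaries.

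**What to change.** In 2.13.6 (Vital signs), extend the named variables to supine blood pressure, pulse rate, respiratory rate and oxygen saturation. State that they are summarised by treatment and time point with the statistics already listed. State also that the number and percentage of out-of-range values, against the investigator reference range already used for flagging, cover all four variables. Optionally, give each subject's lowest recorded oxygen saturation after the first morphine dose, by treatment and as description only.

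Separately, reconcile section 2.3.1 (saturation on clinical indication) with the synopsis, section 2.3.2 and the Table 1 footnote (fixed time points, or monitoring from 2 h), and say which saturation readings are stored as data. Which monitoring rule applies is for the sponsor and the investigator to settle.

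The analysis change costs one line of text and one extra table. It needs no new assessment, and section 2.15.1 classes statistical analyses beyond those described as non-substantial.

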#### **ECG**

At each time point, absolute values and change from baseline of ECG numeric variables will be summarized with the number of samples (n), mean, SD, SEM, median, Min, and Max values. The number of available observations and out-of-range values (absolute and in percentage) will be presented. Values outside the investigator's normal range will be flagged in the listing. 'H' and 'L', denoting values above or below the investigator reference range (when present), will flag out-of-range results.

#### Clinical laboratory tests

At each time point, absolute values and change from baseline of clinical laboratory variables will be summarized with n, mean, SD, SEM, median, Min, and Max values. The number of available observations and out-of-range values (absolute and in percentage) will be presented. All laboratory data (including re-check values if present) will be listed chronologically. 'H' and 'L', denoting values above or below the investigator reference range (when present), will flag out-of-range results.

### Analysis of pharmacokinetic endpoints

The individual plasma nortriptyline, morphine, and M6G concentrations will be listed by treatment, subject, visit and time. Individual plasma drug concentrations versus time will be plotted in panel plots for each treatment using both a linear and log y-axis.

The individual plasma morphine and nortriptyline concentrations will be summarised (number of samples [n], mean, standard deviation [SD], % coefficient of variation [CV], median, minimum [Min] and maximum [Max] values) by treatment and time, and will also be presented graphically as mean over time, with standard deviation as error bars.

When an actual sampling time of a drug concentration sample differs from the protocol time by more than 10% and at least 5 minutes, the concentration will be excluded from calculation of descriptive statistics and a note will be added to the sample in the listing. A sample will in general not be excluded from the non-compartmental analysis due to deviation from the protocol sampling times.

The individual PK parameters (except tmax and tlag) will be summarized (n, mean, SD, %CV, geometric mean, geometric %CV, median, Min and Max) per treatment group and will be presented graphically as boxplots. For tmax and tlag, the n, median, Min and Max statistics will be reported. The procedure for non-compartmental analysis at CHDR including the post and pre-processing of data is described in SOP SDANCA.

#### Analysis of pharmacodynamic endpoints

The final analysis will be preceded by a blind data review which consists of individual graphs per visit by time of all pharmacodynamic measurements by time. The graphs will be used to detect outliers and measurements unsuitable for analysis. The PD parameters will be listed by treatment, subject, visit and time. Individual graphs by time will be generated.

Repeatedly measured PD endpoints (PainCart® and CNS tests) will be summarised (n, mean, SD, SEM, median, Min and Max values) by treatment and time, and will also be presented graphically as mean over time, with standard deviation as error bars.

Single measured PD endpoints will be summarised (mean, SD, SEM, median, Min and Max values) by treatment, and will also be presented graphically as mean in a bar graph, with standard deviation as error bars.

Parameters will initially be analysed without transformation, but if the data suggest otherwise, log-transformation may be applied. Log-transformed parameters will be back-transformed after analysis where the results may be interpreted as percentage change.

To establish whether significant treatment effects can be detected on the repeatedly measured PD parameters, parameters will be analysed with a mixed model analysis of covariance (ANCOVA) with treatment, time, period and treatment by time as fixed factors and subject, subject by treatment and subject by time as random factors and the (average) baseline measurement as covariate.

Single measured PD parameters will be analysed with a mixed model analysis of variance (ANOVA) with treatment and period as fixed factors and subject as random factor.

The Kenward-Roger approximation will be used to estimate denominator degrees of freedom and model parameters will be estimated using the restricted maximum likelihood method.

The general treatment effect and specific contrasts will be reported with the estimated difference and the 95% confidence interval, the least square mean estimates and the p-value. Graphs of the Least Squares Means (LSM) estimates over time by treatment will be presented with 95% confidence intervals as error bars, as well as change from baseline LSM estimates.

The following contrasts will be calculated within the model:

## morphine + nortriptyline versus morphine

All the collected PD endpoint will be analysed with descriptive statistics. However, only PD endpoints collected after start of the first IV bolus injection will be used for the mixed model ANCOVA analysis.

Final analysis of specific PD endpoints (PainCart® and CNS tests) will be performed in sequence to limit the number of tests. Refer to Table 3 and 4 below. Initially, only the parameters listed in the 'first round analysis' column will be analysed following methods described further along this paragraph.

Only in case one or more of the endpoints listed in the 'first round analysis' column reaches statistical significance in any of the contrasts, the endpoints mentioned in the 'second round analysis' will be analysed. Whether to proceed with the 'second round analysis' is evaluated separately for each test.

Due to the large amount endpoints obtained from pEEG, those results will be analysed separately to allow for comprehensive evaluation of all power bands, EEG-derivations taken together.

BSI endpoints will be presented in a frequency table.

**Table 9.** PainCart® endpoints

PainCart® endpoints			
Test	First round analysis	Second round analysis	
Pain pressure	PDT, PTT	AUC, VAS, McGill	
Heat Pain	PDT	VAS, McGill	
Cold pressor	PDT, PTT	AAC, VAS, McGill	
Electrical stair	PDT, PTT	AUC, VAS, McGill	
Electrical Burst	PDT, PTT	AUC, VAS, McGill	
CPM PDT		NA	

**Table 10.** CNS test endpoints

CNS test endpoints			
Test	First round analysis	Second round analysis	
Adaptive tracker	Average performance	NA	
Body sway	Antero-posterior sway	NA	
VAS B&L	Alertness	Mood; calmness	
VAS Bowdle	Feeling High	- Internal perception	
		- External perception	
N-back	- Average reaction time (ms) (two-	- Average reaction time (ms) (zero- and	
	back)	one-back)	
	- Number of correct targets (two-	- Number of correct targets (zero- and	
	back)	one-back)	
	- Number of incorrect targets (two-	- Number of incorrect targets (zero- and	
	back)	one-back)	
	- Number of faulty non-target	- Number of faulty non-target responses	
	responses (two-back)	(zero- and one-back)	
VVLT	- Delayed recall (number correct)	- Immediate recall trial 3 (number	
		correct)	
		- Delayed recognition (number correct)	
		- Delayed recognition (reaction time)	
Eye Movement	- Saccadic peak velocity	NA	
	(degrees/sec)		
	- Saccadic reaction time (sec)		
	- Saccadic Inaccuracy (%)		
	- Smooth pursuit (%)		
Pupillometry	- Pupil/iris ration (left and right)	NA	
SRT	Reaction time	NA	
STAI	State Anxiety Score	NA	
BSI	- General somatic symptoms	NA	
	- Cognitive symptoms		
	- Depressed mood		
	- Anxiety paranoid thoughts		

	

Global severity index

Interpersonal sensitivity

Hostility

Phobic anxiety

Psychoticism

	
pEEG	Frequency range for spectral analysis (Delta, Theta, Alpha, Beta, Gamma)	NA

